8 ASSESSMENT OF SAFETY

8.1 SPECIFICATION OF SAFETY PARAMETERS

In addition to spontaneous reports of adverse events, subjects will complete a 10 cm discomfort/pain VAS and the principal investigator will examine the treated area and report immediate and short term response.

8.1.1 DEFINITION OF ADVERSE EVENTS (AE) AND ADVERSE DEVICE EFFECT (ADE)

Adverse event means any untoward medical occurrence, unintended disease or injury, or untoward clinical signs (including abnormal laboratory findings) in subjects, users or other persons, whether or not related to the investigational medical device. This definition includes events related to the investigational medical device or the comparator. This definition includes events related to the procedures involved. For users or other persons, this definition is restricted to events related to investigational medical devices (ISO 14155:2011).

Adverse device effect means any adverse event related to the use of an investigational medical device. This definition includes adverse events resulting from insufficient or inadequate instructions for use, deployment, implantation, installation, or operation, or any malfunction of the investigational medical device. This definition includes any event resulting from use error or from intentional misuse of the investigational medical device (ISO 14155:2011).

8.1.2 DEFINITION OF SERIOUS ADVERSE EVENTS (SAE)

NOTE: The term serious is not synonymous with severity, which may be used to describe the intensity of an event experienced by the subject). An AE that does not meet any of the below criteria will be classified as non-serious.

A serious AE is any adverse event that:

- led to death,
- led to serious deterioration in the health of the subject, that either resulted in
 - a life-threatening illness or injury, or
 - a permanent impairment of a body structure or a body function, or

- in-patient or prolonged hospitalization, or
- medical or surgical intervention to prevent life-threatening illness or injury or permanent impairment to a body structure or a body function,
- led to fetal distress, fetal death or a congenital abnormality or birth defect

Planned hospitalization for a pre-existing condition, or a procedure required by the CIP, without serious deterioration in health, is not considered a serious adverse event (ISO 14155:2011).

8.1.3 DEFINITION OF SERIOUS ADVERSE DEVICE EFFECT (SADE)

This definition includes any adverse device effect that has resulted in any of the consequences characteristic of a serious adverse event. Unanticipated serious adverse device effect (USADE) is any serious adverse device effect which by its nature, incidence, severity or outcome has not been identified in the current version of the risk analysis report. Anticipated serious adverse device effect (ASADE) is an effect which by its nature, incidence, severity or outcome has been identified in the risk analysis report (ISO14155:2011).

8.1.4 DEFINITION OF DEVICE DEFICIENCY

Inadequacy of a medical device with respect to its identity, quality, durability, reliability, safety or performance. Device deficiencies include malfunctions, use errors, and inadequate labelling (ISO 14155:2011).

Any Investigational Medical Device Deficiency that might have led to a SAE if a) suitable action had not been taken or b) intervention had not been made or c) if circumstances had been less fortunate is subject to the same reporting requirement of SAEs (MEDDEV 2.7/3 revision 3).

8.2 CLASSIFICATION OF AN ADVERSE EVENT

8.2.1 SEVERITY OF EVENT

For AEs not included in the protocol defined grading system, the following guidelines will be used to describe severity.

- **Mild** – Events require minimal or no treatment and do not interfere with the participant's daily activities.
- **Moderate** – Events result in a low level of inconvenience or concern with the therapeutic measures. Moderate events may cause some interference with functioning.
- **Severe** – Events interrupt a participant's usual daily activity and may require systemic drug therapy or other treatment. Severe events are usually potentially life-threatening or incapacitating.

8.2.2 RELATIONSHIP TO INVESTIGATIONAL DEVICE

The clinician's assessment of an AE's relationship to the investigational device is part of the documentation process, but it is not a factor in determining what is or is not reported in the study. If there is any doubt as to whether a clinical observation is an AE, the event should be reported. All AEs must have their relationship to investigational device assessed. In a clinical trial, the study product must always be suspect. To help assessment, the following guidelines are used.

- **Not Related** – relation to the device or procedure can be excluded when:
 - The event is not a known side effect of the product category the device belongs to or of similar devices and procedures;
 - the event has no temporal relationship with the use of the investigational device or the procedures;
 - the serious event does not follow a known response pattern to the medical device (if the response pattern is previously known) and is biologically implausible
 - the discontinuation of medical device application or the reduction of the level of activation/exposure - when clinically feasible – and reintroduction of its use (or increase of the level of activation/exposure), do not impact on the serious event;
 - the event involves a body-site or an organ not expected to be affected by the device or procedure;
 - the serious event can be attributed to another cause (e.g. an underlying or concurrent illness/ clinical condition, an effect of another device, drug, treatment or other risk factors).
- **Unlikely**: the relationship with the use of the device seems not relevant and/or the event can be reasonably explained by another cause, but additional information may be obtained.
- **Possible**: the relationship with the use of the investigational device is weak but cannot be ruled out completely. Alternative causes are also possible (e.g. an underlying or concurrent illness/ clinical condition or/and an effect of another device, drug or treatment). Cases where relatedness cannot be assessed or no information has been obtained should also be classified as possible.
- **Probable**: the relationship with the use of the investigational device seems relevant and/or the event cannot reasonably be explained by another cause, but additional information may be obtained.
- **Causal relationship**: the serious event is associated with the investigational device or with procedures beyond reasonable doubt when:
 - the event is a known side effect of the product category the device belongs to or of similar devices and procedures;
 - the event has a temporal relationship with investigational device use/application or procedures;
 - the event involves a body-site or organ that the investigational device or procedures are applied to or the investigational device or procedures have an effect on;
 - the serious event follows a known response pattern to the medical device (if the response pattern is previously known);
 - the discontinuation of medical device application (or reduction of the level of activation/exposure) and reintroduction of its use (or increase of the level of activation/exposure), impact on the serious event (when clinically feasible);
 - other possible causes (e.g. an underlying or concurrent illness/ clinical condition or/and an effect of another device, drug or treatment) have been adequately ruled out;
 - harm to the subject is due to error in use;

8.2.3 EXPECTEDNESS

Expected (anticipated) adverse reactions are AEs that are common and known to occur for the investigational device being studied. Expected adverse events in this study include discomfort or significant pain post-treatment, excessive skin redness (erythema) and/or swelling (edema), in-grown hairs, damage to natural skin texture (crust, blister, burn), change of pigmentation (hyper- and hypo-pigmentation), scarring. Treatment of hair-bearing areas in males may result in some damage to the follicles and subsequent loss of hair.

An AE or suspected adverse reaction is considered "unexpected" (unanticipated) if it is not known to occur for the investigational device being studied and at the specificity or severity that has been observed (AE not described into the Clinical protocol or User Manual).

8.3 TIME PERIOD AND FREQUENCY FOR EVENT ASSESSMENT AND FOLLOW-UP

The occurrence of an AE or SAE may come to the attention of study personnel during study visits and interviews of a study participant presenting for medical care, or upon review by a study monitor. All AEs including local and systemic reactions not meeting the criteria for SAEs will be captured on the appropriate CRF. Information to be collected includes event description, time of onset, clinician's assessment of severity, relationship to investigational device and study procedures (assessed only by those with the training and authority to make a diagnosis), and time of resolution/stabilization of the event. All AEs occurring while on study must be documented appropriately regardless of relationship. All AEs will be followed to adequate resolution.

Any medical condition that is present at the time that the participant is screened will be considered as baseline and not reported as an AE. However, if the study participant's condition deteriorates at any time during the study, it will be recorded as an AE.

Changes in the severity of an AE will be documented to allow an assessment of the duration of the event at each level of severity to be performed. AEs characterized as intermittent require documentation of onset and duration of each episode.

The PI will record all adverse events with start dates occurring any time after informed consent is obtained. At each study visit, the investigator will inquire study subjects about the occurrence of AE/SAEs since the last visit. All adverse events need to be followed until resolution or until study end, whichever occurs first.

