I will conduct the trial in accordance with the clinical investigation plan, Good Clinical Practice guidelines, ISO 14155:2011 (Clinical Investigation of Medical Devices for Human Subjects - Good Clinical Practice), as well as local regulations. I also accept respective revisions to the clinical investigation plan approved by authorized personnel of the Sponsor and by regulatory authorities.

Institution:

[name] [name]

Principal Investigator (Printed name)

Principal Investigator (Signature)

22/2/18

Date

PROTOCOL SUMMARY

TITLE	Clinical Evaluation of the Safety and Performance of Fractional RF for the Treatment of Surgical Scars Following Breast Augmentation, Abdominoplasty or Face Lift
SUMMARY	Split-body/face evaluator-blind study of the safety and performance of fractional RF for the treatment of surgical scars following breast augmentation, abdominoplasty or face lift. The study will enroll up to 50 female subjects requesting treatment of surgical scars following breast augmentation or abdominoplasty and up to 25 male and female subjects requesting treatment of surgical scars following face lift surgery. Subjects will receive a total of three treatments of their surgical scars at one-month intervals on one side of the body or facial incision only. Subjects will be followed up at one, two, three and ten months after their last treatment. Analysis will be performed on all subjects who receive at least one treatment. Outcomes will be compared to the non-treated side.
OBJECTIVES	The objective of this clinical study is to evaluate the safety and performance of fractional RF for the treatment of surgical scars following breast augmentation, abdominoplasty or face lift.

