2.3 POTENTIAL RISKS AND BENEFITS

2.3.1 KNOWN POTENTIAL RISKS

The potential risks for adverse events of the treatment procedure include but are not limited to discomfort or significant pain post-treatment, excessive skin redness (erythema) and/or swelling (edema), in-grown hairs, damage to natural skin texture (crust, blister, burn), change of pigmentation (hyper- and hypo-pigmentation) and scarring. Treatment of hair-bearing areas in male patients may result in some damage to the follicles and subsequent loss of hair. Avoid the beard area and other hair-growing zones if the patient does not wish to experience hair growth reduction.

Further information about residual risks associated with the device and with participation in the clinical investigation are reported in the device User Manual.

Residual risks will be mitigated as follows:

- Selection of Investigator with experience in the therapeutic area of the clinical investigation
- Investigator will undergo training prior to patients' enrollment
- For the first procedure of each site, an experienced person with the use of the device, representing the sponsor, will attend.
- Patients will be rigorously screened prior to their enrollment
- Patients will be rigorously followed over the course of the study

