4.2.2 SECONDARY PERFORMANCE ENDPOINTS

- Improvement in appearance of surgical scars at 1 and 2 months post-treatment as evaluated by independent blinded reviewer using the General Aesthetic Improvement Scale (GAIS) and Manchester Scar Scale (MSS).
- Assessment of surgical scars at 3 and 10 months post-treatment as evaluated by independent blinded reviewer using the Patient and Observer Scar Assessment Scale (POSAS).
- Assessment of surgical scars at 3 and 10 months post-treatment as evaluated by the subject using the Patient and Observer Scar Assessment Scale (POSAS).
- Subjects' assessment of satisfaction (5-point Likert Scale) with the treatment at 3 and 10 months post-treatment.

Safety endpoints:

- Subject's assessment of discomfort and pain after treatment as measured by a 10 cm visual analog scale (VAS).
- Subjects experiencing a treatment-related adverse event (AE) by 10 months post-treatment.

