7.3.2 ENROLLMENT/BASELINE

Enrollment/Baseline Visit (Visit 2, Day 0)

Once a subject has been confirmed that they continue to meet inclusion/exclusion criteria, they will receive a unique identifying number that will be composed of a two-digit site number and a two-digit subject number in sequence. This unique identifier will be used throughout the entire study and will be entered in the subject's case report form (CRF). The investigator will confirm that the subject still meets the inclusion/exclusion criteria. Vital signs and demographics will be collected and a physical exam will be performed. The subject will complete the POSAS.

Photography

Photographs will be taken prior to first treatment and throughout the study according to specified time points detailed in the Schedule of Events Table (section 7.3.7), utilizing standard scientific equipment. Two sets of photographs will be required, one set for the treated side of the body/face and a second set for the untreated side of the body/face.

The photos should be taken in a private room or area of the clinic under controlled conditions, including the distance, angle, background and lighting in order to achieve high-quality sets of photographs. Direct illumination will not be used. The subject should be placed in the same position each time. As each photograph is taken, it should be viewed to ensure that it is in focus and is similar to its baseline counterpart in all technical aspects, including lighting, distance and angle.

For consistency purposes, the same person should ideally take all study photographs, especially per subject. The digital files should follow a consistent standard naming scheme.

Treatment

Subjects will receive treatment as described in section 7.3.1. Only one side of the body/face will be treated. The same side will be treated for the duration of the study. Only half of a scar will be treated

and remaining half will serve as the control. Following treatment, the investigator will examine the treated area and report immediate and short term response. Subjects will complete the 10 cm discomfort/pain VAS immediately after treatment. A new disposal tip will be used for each patient treatment.

Treatment procedure should include positioning of the patient in a manner that enables comfortable access to the treated anatomical site.

Assessment

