10.4.4 SAFETY ANALYSES

The safety analysis will be done by analyzing spontaneous reports of adverse events (AE), subjects' completed 10 cm discomfort/pain VAS and a response questionnaire as well as analysis of immediate and short term response reports by the principal investigator from his/her observation/examination of the treated area. Appropriate Medical Dictionary for Regulatory Activities (MedDRA) code will be used to describe all spontaneously reported or other study related adverse events.

Summaries of spontaneously reported or other study related adverse events will be presented as:

- Number (%) of subjects with any AE,
- Number (%) of subjects with any serious adverse events (SAE),
- Number (%) of subjects permanently withdrawn from treatment due to AE

Summaries of analysis of immediate and short term response reports by the principal investigator examination will be displayed on a bar or pie chart as;

- the overall frequency of subjects with each event (pain during treatment, hemorrhage, burn, erythema, edema, purpura)
- Frequency of subjects with specific severity/intensity for each event using a 5 points scale: 1=none; 2=trace; 3=moderate; 4=marked; 5=severe
- The overall percentage or proportion of subject observed with marked or severe intensity of any event will be calculated and compared to those with none, trace or moderate severity/intensity with the aid of a bar or pie chart.

The following will be considered for the analysis of 10 cm discomfort/pain VAS scores safety data:

Summary table for differences of baseline post-treatment (Visit 2) and Visit 6 post-treatment 10 cm discomfort/pain VAS scores will be displayed as mean difference, standard deviation and standard error. The 10 cm discomfort/pain VAS is a 11-level (0 to 10) ordinal scale tool for assessing pain.

Bar, pie charts or graphs indicating scores, percentages or proportions of subjects with Visit 6 and baseline (Visit 2) post-treatments VAS scores difference that is < 1 and > 1 will be used to analyse subjects' tolerability of this treatment.

All statistical tests will be two-sided. The level of statistical significance for effectiveness analyses is 5% ($\alpha = 0.05$) for all tests of differences. Where appropriate, Paired t-test and/or Wilcoxon Signed-Ranks Test

for Matched Pairs will be used to compare the difference between Visit 2 and Visit 6 post treatment VAS scores.

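### The side of a local adverse event is not a required data item and no safety summary compares the halves, so relatedness of late scar changes rests on unblinded judgement although a concurrent control exists

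*Combined protocol and SAP*

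**What the plan says.** - **The control.** The Protocol Summary states: "Outcomes will be compared to the non-treated side". It makes no exception for safety. Section 7.3.2 says that half of a scar is treated and the "remaining half will serve as the control".
- **Safety endpoint (listed in section 4.2.2).** "Subjects experiencing a treatment-related adverse event (AE) by 10 months post-treatment".
- **AE data items.** Section 8.3: "Information to be collected includes event description, time of onset", followed by severity, relationship to the device and to study procedures, and time of resolution or stabilisation. Section 8.4.1 names start and stop dates, severity and relatedness. Neither list names side or location.
- **AE summaries (section 10.4.4).** "Number (%) of subjects with any AE", then subjects with any SAE and subjects withdrawn because of an AE. No summary is by half, and none is listed for the treatment-related endpoint itself. The only safety test compares the pain VAS at Visit 6 with Visit 2.
- **Expected local risks.** Section 2.3.1 includes redness, damage to skin texture, "change of pigmentation (hyper- and hypo-pigmentation) and scarring".
- **Causality.** Section 8.2.2 gives criteria from not related to causal. It adds: "Cases where relatedness cannot be assessed or no information has been obtained should also be classified as possible". Under section 10.6.2 only the independent reviewers are blinded.
- **Entry and follow-up.** Section 5.2 admits scars from four weeks after surgery, and participation lasts 12 months.

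**The concern.** Several of the listed device risks are also things a young surgical scar can do untreated: stay red, change pigment, change texture, or heal worse. A within-subject control exists to show how much of that would have happened anyway. If the side of a local event is not captured in analysable form and the halves are not compared, the trial can report how many subjects had such an event but cannot set that figure against the untreated half.

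The error can run either way. Natural worsening on the treated half may be counted as a device effect, or a real device effect may be put down to the scar's natural course. The concern is confined to late local changes. Burns or swelling straight after a pulse should have little background rate.

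**Working it through.** The documents give no AE rate and no safety sample size, so there is no stated figure to reproduce. The check is a comparison of the text, followed by arithmetic with assumed rates.

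**1. Where could the untreated half enter the safety data?**

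| Step | Section | Untreated half used? |
|---|---|---|
| Immediate and 30-minute response | 7.3.2, 8.1 | No, treated area only (reasonable for an acute check) |
| AE enquiry at visits | 7.3.3, 8.3 | Any AE is reportable, but inspection of both halves is not stated |
| AE data items | 8.3, 8.4.1 | Side not required |
| Relatedness | 8.2.2 | Body site and other causes considered, but side not kept as data |
| AE tables | 10.4.4 | No, per subject |
| Safety test | 10.4.4 | No, Visit 6 against Visit 2 |

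Section 8.3 also records deterioration of a condition present at screening as an AE, with no reference to side. Worsening on either half thus enters the same per-subject count.

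**2. Treated-half events with no device effect.** Let b be the background probability of a late local event per half (assumed 5-20%) and N the number of subjects. The expected number is N × b. Section 10.5 plans 15 per cohort in three cohorts, so 3 × 15 = 45. The enrolment cap is 50 + 25 = 75.

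- N = 45: 45 × 0.05 = 2.25 and 45 × 0.20 = 9, so about 2-9.
- N = 75: 75 × 0.05 = 3.75 and 75 × 0.20 = 15, so about 4-15.

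These bound the misattributed cases from above, since the causality criteria would remove some.

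**3. What a per-subject count can distinguish.** With t the probability on the treated half and the halves independent, the chance of an event on either half is 1 − (1 − b)(1 − t).

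- b = 0.10, no device effect (t = 0.10): 1 − 0.90 × 0.90 = 0.190, or 14.2 of 75.
- b = 0.05, device adds 10 points (t = 0.15): 1 − 0.95 × 0.85 = 0.1925, or 14.4 of 75.

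The counts are almost the same, but the treated-minus-untreated differences are 0 and 10 points. If events always coincide on both halves, the first case gives 10%. If every untreated-half event is matched on the treated half, the second gives 15%. The overlap of about 19% therefore depends on the assumed independence.

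**4. What a by-half comparison could deliver.** Assume 15% treated, 5% untreated, independent halves. The discordant probabilities are 0.15 × 0.95 = 0.1425 and 0.05 × 0.85 = 0.0425, summing to 0.185. The standard error of the paired difference is √[(0.185 − 0.10²)/N].

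- N = 75: √(0.175/75) = 0.048; 95% half-width 1.96 × 0.048 ≈ 0.095.
- N = 45: √(0.175/45) = 0.062; 95% half-width 1.96 × 0.062 ≈ 0.122.

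Exact McNemar power for this case is about 43% at 75 and 22% at 45. The comparison is worth estimating, but it is not a powered test.

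**The case against.** The best defence is that the plan already protects attribution.

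- **Recording.** Section 8.3 captures all AEs, local and systemic, regardless of relationship, with a description that could state the location. Section 10.4.10 lists individual data. A reader might infer that side will go unrecorded. The documents do not show that: the CRF is not among them, and free text may carry it. What stands is that side is not required, so it cannot be relied on for a table.
- **Causality.** Section 8.2.2 counts against relatedness an event at a body site the device should not affect, and an event reasonably explained by another cause. A causal rating looks for other causes to have been ruled out. The clinician also knows which half was treated. A reader might infer that every background event would be rated at least possible. That default covers only cases that cannot be assessed or lack information. The criteria do help with events confined to the untreated half. They help less with natural worsening on the treated half, where site and timing fit the device and the event is on the expected list in section 8.2.3.
- **Baseline rule.** Under section 8.3, conditions present at screening are not AEs, so redness or pigment change already there is excluded. Later deterioration is not.
- **Treated-area examination.** This is an acute check after the pulse. It is sensible as written and is not evidence of a wasted control.
- **Any-AE table.** It makes no claim about the device. The issue bears on the treatment-related endpoint.
- **Blinded scar scores.** MSS and POSAS, with photographs of both sides (section 7.3.2), could show worse scarring by half. However, the hypotheses in section 10.2 compare post-treatment with baseline, not the two halves, and no AE reading from photographs is planned.

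**Conclusion.** The point holds as a gap in required data and planned analysis. Side is not a required item for local AEs, and no safety summary compares the halves, although the untreated half is the stated control. For late redness, pigment, texture and scar changes, the treatment-related endpoint rests on unblinded causality judgement. Existing safeguards lower the risk of misattribution in either direction but do not replace the concurrent comparison.

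The size is unknown. The ranges of 2-9 of 45 and 4-15 of 75 rest on an assumed 5-20% background per half and are upper bounds, not forecasts. Reading them as expected false device harms would go beyond the documents, which give no background rate. This is an inexpensive improvement that should be made; it does not invalidate the safety assessment.

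**What to change.** 1. Add a required AE CRF field for local events: treated half, untreated half, both, or boundary/unclear. Name it in sections 8.3 and 8.4.1.
2. State in section 7.3.3 that both halves are inspected in the same way when AEs are assessed at the existing follow-up visits. Leave the immediate and 30-minute response check on the treated area.
3. In section 10.4.4, tabulate late local AEs by half, with the paired difference in the proportion of subjects affected and its 95% confidence interval. Label it descriptive estimation, not a powered test.

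**Cost.** One CRF field, a short additional inspection at visits already planned, and one table. No extra subjects or visits are needed. Minor events on the untreated half must now be recorded, side may be unclear near the midline of a shared scar, and the interval will be wide (about ±9 to ±12 points in the example worked above). The field has to be in place during follow-up: side is hard to reconstruct reliably afterwards, and section 7.3.4 offers treatment of the untreated side once the study ends.

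### Section 10.4.4 codes and tabulates a narrower set of adverse events than section 8.3 collects, so the any-AE and any-SAE percentages can be too low

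*Combined protocol and SAP*

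**What the plan says.** The combined protocol and SAP treats AE collection and AE analysis in separate places.

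**Collection**
- Section 8.3 provides for active enquiry: "At each study visit, the investigator will inquire study subjects about the occurrence of AE/SAEs since the last visit". It also states: "All AEs occurring while on study must be documented appropriately regardless of relationship".
- Section 7.3.3 adds an examination for AEs 2-3 days after each treatment, at Visits 3, 5 and 7.
- Section 8.4.1 puts every AE on the CRF with its dates, severity and relatedness.
- Section 8.2.2 says of the clinician's relatedness assessment that "it is not a factor in determining what is or is not reported in the study".

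**Analysis**
- Section 8.1 introduces the safety parameters with "In addition to spontaneous reports of adverse events", followed by the pain VAS and the investigator's response assessment.
- Section 10.4.4 opens: "The safety analysis will be done by analyzing spontaneous reports of adverse events (AE".
- For coding, it says the MedDRA "code will be used to describe all spontaneously reported or other study related adverse events".
- For the tables, it says: "Summaries of spontaneously reported or other study related adverse events will be presented as". The rows beneath are any AE ("Number (%) of subjects with any AE"), any SAE, and permanent withdrawal from treatment due to an AE.

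The AE safety endpoint in section 4.2.2 is the subject with a treatment-related AE by 10 months. Section 10.4.4 has no row for it.

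**The concern.** The plan records one set of events and says it will analyse a smaller one. On the literal wording, an event enters the tables by either of two routes: the subject volunteered it, or it was judged study related. An event that came to light only because the investigator asked or examined, and that was then judged unrelated, takes neither route. It stays on the CRF, uncoded and uncounted, while the row is still labelled as any AE.

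For those events, inclusion rests on a relatedness judgement. It is made at the site, and section 10.6.2 blinds only the independent reviewers. This sits badly with section 8.2.2, which says relatedness should not decide what is reported.

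The SAE row shows the conflict most plainly. Section 8.4.2 makes every SAE reportable whether or not it is related to the device or procedure, but the any-SAE row falls under the restricted heading. The SAE count in the study report could then differ from the count sent to the authorities.

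The restricted set serves neither purpose that an AE table normally has. It is not all AEs, and it is not the treatment-related AEs that form the endpoint.

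**Working it through.** The documents state no AE rate, so there is no figure of the plan's own to reproduce. The check is a comparison of sections, followed by an illustration under assumptions.

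**Which recorded events are counted (literal reading of section 10.4.4)**

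| How the event came to light | Judged related | Judged unrelated |
|---|---|---|
| Volunteered by the subject | counted | counted |
| Elicited by enquiry, or found on examination | counted | not counted |

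Sections 8.3 and 8.4.1 put all four cells on the CRF. Only one cell drops out of the tables. The restricted count can therefore equal the full count or fall below it, but cannot exceed it.

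**Illustration of size**

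Inputs:
- N = 50 + 25 = 75, the enrolment ceiling in section 5.1. The analysis set in section 10.3 may be smaller.
- a = probability that a subject has at least one AE that is volunteered or study related (assumed).
- u = probability that a subject has at least one AE that is elicited and judged unrelated (assumed).
- The two are taken as independent (assumed).

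Formulas:
- Proportion shown under the literal wording: a
- Proportion with any recorded AE: 1 − (1 − a)(1 − u)
- Shortfall: the difference, (1 − a)u

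Example with a = 0.30 and u = 0.30: all recorded AEs give 1 − 0.70 × 0.70 = 0.51, against 0.30 shown. The shortfall is 0.70 × 0.30 = 0.21, and 0.21 × 75 = 15.75, or about 16 subjects.

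Shortfall in percentage points:

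| a | u = 0 | u = 0.1 | u = 0.3 | u = 0.5 |
|---|---|---|---|---|
| 0.10 | 0 | 9 | 27 | 45 |
| 0.30 | 0 | 7 | 21 | 35 |
| 0.60 | 0 | 4 | 12 | 20 |
| 0.90 | 0 | 1 | 3 | 5 |

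For u above zero the range is 1 to 45 points, or 0.75 to 33.75 of 75 subjects. The shortfall is zero if no subject has an elicited, unrelated event, or if every subject with one also has an event that counts. It shrinks as a rises, because one counted event is enough to place a subject in the row. Nothing in the documents favours one cell of this table over another.

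**The case against.** The strongest defence is that the restricting phrase is loose drafting and was not meant as a filter. Study related is not a defined term in the plan: section 8.2.2 grades relationship to the investigational device, and section 4.2.2 speaks of treatment-related events. The phrase could mean any other event arising in the study, and the rows carry no relatedness qualifier. Mention of spontaneous reports may serve only to separate AE CRF events from the VAS and the investigator's response scale.

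This has force, and it means that undercounting is a possibility and not a certainty. It does not settle the matter. On the broad reading, naming spontaneous reports in the coding and table sentences would add nothing. If both readings are open, two programmers can produce different any-AE counts from the same data.

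The plan also has safeguards:
- Section 8.2.2 says the product is always to be suspected, and events that cannot be assessed are classed as possibly related.
- Section 8.4.2 has every SAE reported to the sponsor.
- Section 10.4.4 summarises the investigator-observed reactions (pain, burn, erythema, edema, purpura, hemorrhage) separately, with no relatedness filter. These cover only the immediate and 30-minute response.
- Section 10.4.10 promises individual listings, but it does not name AEs, and a listing does not correct a percentage in a table.

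A correct judgement that an event is unrelated would keep it out of the treatment-related endpoint under any wording. That endpoint needs an unblinded relatedness judgement in any case, and the rewording does not remove it.

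**Conclusion.** The mismatch is real and should be corrected. Followed literally, section 10.4.4 leaves elicited events judged unrelated out of rows labelled as any AE and any SAE, against sections 8.2.2, 8.3 and 8.4.1. Any resulting error lowers the percentage. Its size cannot be derived from the documents and may be zero; the range in the working rests wholly on assumed rates and independence.

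A reader might infer three stronger things, which the documents do not support:
- **That the reported AE rate will be too low, making the device look safer than it is.** This needs the literal reading and at least one subject whose only events are elicited and judged unrelated. A misleading picture of device safety would further require that such events be misjudged, and the documents give no evidence of that.
- **That the whole any-AE rate depends on an unblinded relatedness judgement.** Volunteered events count whatever their relationship. The judgement decides inclusion only for elicited events.
- **That subjects are examined for AEs at every visit.** Enquiry is at every visit. Examination for AEs is stated for Visits 3, 5 and 7, apart from the response check after each treatment.

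A separate gap does not depend on how the phrase is read: section 10.4.4 has no row for the treatment-related AE endpoint.

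**What to change.** 1. In section 10.4.4, replace the restricting phrase, for both MedDRA coding and the tables, with: *all adverse events recorded on the CRF under section 8.3, whether volunteered, elicited or found on examination, and regardless of relationship*.
2. Make the matching change where sections 8.1 and 10.4.4 name spontaneous reports as the source of AEs.
3. Add a row to the AE summary for the number and percentage of subjects with a treatment-related AE by 10 months, to match section 4.2.2.

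The cost is wording and one table row. Sections 8.3 and 8.4.1 already collect the events and their relatedness, so no new data and no extra visits are needed. The one downside for the sponsor is that the stated AE percentage may be less favourable.
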